1 INTRODUCTION

1.1 STUDY BACKGROUND AND RATIONALE

Approximately 19-34 % of all people with diabetes will at some time in life develop a diabetic foot ulcer (DFU).¹ People with diabetes are especially prone to develop foot ulcers because of different diabetic complications, especially angiopathy and peripheral neuropathy.

The DFUs are often hard to heal and the treatment is long-lasting. The DFUs result in lower physical and mental quality of life and affects social relationships.² The treatment is also very costly,^{1, 3} it has been estimated that 25-50 % of diabetic inpatient care is related to DFUs.⁴ Despite extensive treatment, all DFUs do not heal but some end in amputation. People with diabetes are at a 25-fold risk of amputation and every 20 second a person somewhere in the world has the foot amputated because of diabetes.⁵ 85 % of these amputations are preceded by a foot ulcer⁶ and many of these ulcers and amputation could have been prevented.⁷

Total contact cast (TCC) as gold standard treatment of DFUs

Plantar DFUs often are the result of a combination of foot deformities that increase plantar pressures when the person walks and that the person keeps walking despite high pressure and ulcers because he or she has lost sensation in the feet because of sensory neuropathy. Literature reviews and international guidelines^{8,9} recommend non-removable knee-high offloading devices, for example, a total contact cast (TCC) to treat plantar DFUs, as this offloads the ulcer from mechanical loading all day and night. Still, TCC is not accepted by all patients and is contraindicated in a number of cases because of negative side-effects. Most of these side-effects are the consequences of immobilizing the ankle joint, which impairs gait and results in lower ambulatory activity. For example, side-effects include reduction of joint flexibility, weight gain, muscle atrophy, sick leave from work and social isolation.¹⁰ In addition, a TCC can give secondary ulcers why weekly visits to the hospital is necessary to change casts. For these reasons, TCC is only used for a minority of the patients for whom it could be beneficial, despite being the gold standard treatment.¹¹

For working patients, casting often means sick leave from work, but casting can also be difficult for older patients with impairments of gait and balance. For patients where TCC is contraindicated or not tolerated, guidelines recommend removable offloading devices despite it is well known that these devices are not very effective.⁸ In practice, this means that many patients do not receive effective treatment. Another problem is that many patients get new foot ulcers after treatment with TCC,¹² in part because adherence to using therapeutic footwear after healing is lower than desirable.¹³

Sealed therapeutic shoe as alternative treatment

The investigators have developed a new treatment concept, sealed therapeutic shoe, which potentially can fill the need for effective ulcer treatment without limiting ambulatory activity with its associated negative consequences for physical, mental and social health, and to a lower cost, resulting in fewer obstacles for clinical use.

The concepts include therapeutic shoes with custom-made insoles, where the new part is how the insole is optimized to offload the ulcer from mechanical loading and that the shoe is "sealed" with a soft plastic strap and is used day and night, like a cast, and is only removed when changing the ulcer dressings. The ulcer is thereby offloaded but the person is free to ambulate and work as usual, and no cast changes are necessary. In addition to effective ulcer treatment and fewer side-effects the investigators hope that the

positive experience of that high adherence to using therapeutic shoes results in healing will lead to higher adherence after healing, and thereby reduction of the risk of ulcer recurrences in the future. The method to offload foot ulcers was first tested in a case-study, where the investigators found that the shoe and insole effectively offloaded the ulcer.¹⁴ After this, the whole sealed shoe concept was evaluated in a feasibility study¹⁵ on seven people with DFU. All ulcers healed and complications were few. The investigators are now going to evaluate the effects of sealed therapeutic shoes compared to gold standard treatment, that is, TCC.

1.2 HYPOTHESES AND OBJECTIVES

The overarching objective is to evaluate whether sealed shoe can heal DFU at least as effectively as TCC, but with fewer adverse events during the treatment period, better long-term effects and to a lower cost.

Specific objectives

Objective 1. To investigate whether a sealed shoe can heal DFUs at least as effectively as TCC (non-inferiority, one-sided hypothesis testing).

Objective 2. To investigate whether there is a difference in adverse events during the treatment period with sealed shoe and TCC (superiority, two-sided hypothesis testing).

Objective 3. To investigate whether there is a difference in long-term effects (up to 12 months after end of treatment) with sealed shoe and TCC (superiority, two-sided hypothesis testing).

Objective 4. To investigate whether there is a difference in health economic outcomes between treatment with sealed shoe and TCC (superiority, two-sided hypothesis testing).

The null hypotheses are that a sealed therapeutic shoe does not heal DFUs at effectively as TCC, and that there are no differences between sealed shoe and TCC in side-effects, long-term effects and health economic outcomes.

2 STUDY METHODS

2.1 OVERALL DESIGN

The study is a randomized controlled trial with two parallel groups (intervention group using sealed shoe and control group using TCC) and an allocation ratio of 1:1.

2.2 RANDOMIZATION

The randomization will be stratified for study site and ulcer area (smaller or bigger than 1 cm², ulcer size calculated as longest diameter*longest perpendicular diameter) and use random permuted blocks of randomly varying size. The randomization details are stored on a protected server of Region Örebro County and cannot be accessed by those who provide clinical input to the SAP.

2.3 SAMPLE SIZE

The sample size calculation was performed using <http://powerandsamplesize.com/Calculators/Compare-2-Proportions/2-Sample-Non-Inferiority-or-Superiority>. Primary outcome is proportion of healed ulcers after 12 weeks of treatment. Based on the literature and our feasibility study the proportion of healed ulcers after 12 weeks treatment is estimated to 90% with sealed shoe or TCC.^{15, 16} If accepting $p=0.05$, a statistical power of 80% and a non-inferiority limit of 10%, 112 participants are

needed. To compensate for attrition of participants during the long-term follow up of secondary outcomes, the aim is to recruit 150 participants. The participants will be randomized to treatment with sealed therapeutic shoe or TCC. However, if it turns out that it is too difficult to recruit 150 participants, the recruitment of participant will end when the primary end point (healing at 12 weeks) has been observed for 56 participants per group, giving a total of 112 which fulfils the sample size calculation.

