Aim 2. To investigate whether there is a difference in adverse events during the treatment period with sealed shoe and TCC.

Aim 3. To investigate whether there is a difference in long-term effects (up to 12 months after end of treatment) with sealed shoe and TCC.

Aim 4. To investigate whether there is a difference in health economic outcomes between treatment with sealed shoe and TCC.

The null hypothesis is that a sealed therapeutic shoe does not heal DFUs as effectively as TCC, and that there are no differences between sealed shoe and TCC in adverse events, long-term effects and health economic outcomes.

Methods

The study is a non-inferiority multicenter randomized controlled trial (RCT).

Participants

Inclusion criteria: at least 18 years old, diagnosed diabetes mellitus (all types) and foot ulcer under metatarsal heads. A foot ulcer is here defined as "a break of the skin of the foot that includes minimally the epidermis and part of the dermis."¹⁵

Exclusion criteria: large ulcers (covering 3-5 metatarsal heads), toe pressure or TcPO₂ <30 mmHg, infection of IWGDF grade 3 (if uncontrolled or treatment has not been administered) or IWGDF grade 4, life expectancy <1 year, active Charcot foot, need of custom-made shoe,

and inability to read or write Swedish. In addition, people will be excluded where dementia, language- or other communication difficulties, active alcohol or substance abuse, or other factors increase the risk that adverse events will not be noted or reported, if the person does not have adequate social support.

The study is a randomized controlled non-inferiority trial where it will be investigated whether a new intervention (sealed shoe) is at least as effective as the established intervention (TCC).

Primary outcome is proportion of healed ulcers after 12 weeks of treatment. Based on the literature and our feasibility study the proportion of healed ulcers after 12 weeks treatment is estimated to 90% with sealed shoe or cast.^{16,17} If accepting $p=0.05$, a statistical power of 80% and a non-inferiority limit of 10%, 112 participants are needed. To compensate for attrition of participants, the aim is to recruit 150 participants. However, if it turns out that it is too difficult to recruit 150 participants, the recruitment of participant will end when the primary end point (healing at 12 weeks) has been observed for 56 participants per group, giving a total of 112 which fulfills the sample size calculation.

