3 STATISTICAL PRINCIPLES

3.1 CONFIDENCE INTERVALS AND P VALUES

In all analyses a 95% confidence level will be used as a cut off to declare statistical significance, and report both exact p-values and 95% CI. One-sided tests and CI will be used for the primary outcome and two-sided tests and CI the secondary outcomes. No adjustment for multiple comparisons will be used.

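### The sample-size formula gives 112 per group, not 112 in total: power is about 55% at 56 per group and about 65% at 150 randomised, not 80%.

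*SAP*

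**What the plan says.** SAP 2.3 bases the sample size on healing at 12 weeks: "the proportion of healed ulcers after 12 weeks treatment is estimated to 90% with sealed shoe or TCC". It continues: "If accepting $p=0.05$, a statistical power of 80% and a non-inferiority limit of 10%, 112 participants are" needed. The protocol's sample-size paragraph (Methods, Participants) says the same: "a statistical power of 80% and a non-inferiority limit of 10%, 112 participants are needed".

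Both documents treat 112 as the whole trial. The aim is to recruit 150, but if that proves too difficult, recruitment ends when the primary endpoint has been "observed for 56 participants per group, giving a total of 112 which fulfils the sample size calculation".

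Other SAP sections settle how the test is run:

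- Section 1.2 makes the primary comparison one-sided non-inferiority.
- Section 3.1 states "In all analyses a 95% confidence level will be used as a cut off to declare statistical significance" and "One-sided tests and CI will be used for the primary outcome", so the type I error is one-sided 0.05.
- Section 2.1 sets two parallel groups with 1:1 allocation.

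**The concern.** The number 112 is what the two-sample non-inferiority formula returns for one group under the stated inputs. The documents split it across two groups, so the design has half the participants its own calculation requires.

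Two things follow. First, the 80% power claimed for the primary endpoint is not delivered at either planned size. Second, the fallback rule rests on this number. Difficulty in recruiting triggers it, but the justification for stopping at 56 per group is that the calculation has been satisfied, and it has not. A trial labelled as having 80% power that then misses non-inferiority could be read as evidence against the shoe, when at these sizes a miss is a common result for two equally effective devices.

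**Working it through.** **Inputs**

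| Quantity | Value | Source |
|---|---|---|
| Healing rate, each arm | 0.90 | SAP 2.3; protocol sample-size paragraph |
| Non-inferiority limit | 0.10, read as an absolute difference | same |
| Type I error | 0.05, one-sided (z = 1.6449) | SAP 2.3, 1.2, 3.1 |
| Power | 0.80 (z = 0.8416) | SAP 2.3; protocol |
| Allocation | 1:1 | SAP 2.1 |
| Planned sizes | 112 total (56 per group); 150 total (75 per group) | SAP 2.3; protocol |

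The documents do not say whether the 10% limit is absolute or relative. The absolute reading is an assumption; it is the one that returns the number 112.

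**Step 1. Reproduce the plan's figure.**

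n per group = [p₁(1−p₁) + p₂(1−p₂)] × (z₀.₉₅ + z₀.₈₀)² / margin²

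= (0.09 + 0.09) × (1.6449 + 0.8416)² / 0.10²

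= 0.18 × 618.26 = 111.29, rounded up to **112 per group, 224 in total**.

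The plan's 112 is reproduced exactly as a per-group number and not as a total.

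**Step 2. Power at the planned sizes.**

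Power(n) = Φ(0.10 / √(0.18/n) − 1.6449)

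- n = 56: 0.10/0.05669 = 1.764; Φ(0.119) = 0.547
- n = 75: 0.10/0.04899 = 2.041; Φ(0.396) = 0.654
- n = 112: 0.10/0.04009 = 2.494; Φ(0.850) = 0.802

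**Step 3. Check without the normal approximation.** Exact binomial enumeration of the chance that the one-sided 95% lower bound exceeds −0.10:

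| Per group | Formula | Exact, Wald bound | Exact, Newcombe bound |
|---|---|---|---|
| 56 | 54.7% | 55.7% | 51.0% |
| 75 | 65.4% | 67.3% | 62.8% |
| 112 | 80.2% | 80.3% | 79.0% |

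**Step 4. Could another reading give 112 in total?** Required number per group under variants:

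- one-sided 0.025: 142
- one-sided 0.10: 82
- continuity correction: 131
- Farrington-Manning variance: 122
- limit of 10% relative to 90%, that is 9 points: 0.18 × 6.1826 / 0.0081 = 137.4, so 138
- superiority test of 90% against 80%: 157 to 219

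None gives 56. Two routes come close. A single-sample variance gives 0.09 × 618.26 = 55.6, but the trial has two arms and SAP 2.3 cites a two-sample calculator. A true advantage for the shoe (93% against 90%) gives 57, but the documents assume 90% with either device.

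**Step 5. The gap.** 224 − 112 = 112 short at the fallback and 224 − 150 = 74 short at the target. With 56 per group, 80% power would need a margin of √(0.18 × 6.1826 / 56) = 0.141, about 14 points.

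**The case against.** The arithmetic is not in dispute, but several qualifications are fair.

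- **How the slip arose is inferred.** The calculator's output is not in the documents. The exact match on 112 is strong evidence that a per-group answer was read as a total, but not proof. The power shortfall does not depend on the cause.
- **The SAP names no risk-difference test.** SAP 6.1.1 reports a risk ratio or odds ratio and sets no margin on either scale. Other readings do not rescue the plan. A risk-ratio limit of 8/9 (0.80/0.90) gives about 61% power at 56 per group and 71% at 75. A 9-point margin gives about 48% and 58%.
- **Power depends on the true healing rate.** If 95% healed in both arms, power would be about 78% at 56 per group and 88% at 75. That is not the rate assumed. In the other direction, SAP 6.1.1 counts a missing 12-week outcome as not healed. If 5% to 10% were missing in both arms (an assumption; no rate is given), power would be about 44% to 38% at 56 per group and 54% to 47% at 75.
- **The attrition allowance.** SAP 2.3 ties the increase to 150 to long-term follow-up of secondary outcomes, so it does not claim a reserve for the primary test. Only the protocol's wording is general. The 150 target is still 74 below 224.
- **Type I error is unaffected.** Non-inferiority shown at these sizes would not be undermined by this mistake.

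These points shape how the power figures should be worded. None makes 112 a correct total.

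**Conclusion.** The concern holds. Under the plan's own assumptions, 80% power needs 112 per group, twice what the documents state. Power is about 55% at the 56-per-group fallback and about 65% at 150 randomised, a shortfall of 25 and 15 percentage points. The type II error is about 45% and 35%, against a stated 20%. These figures rest on 90% healing in both arms, a 10-point absolute margin, one-sided 0.05, equal groups and no missing primary outcomes. The error should be corrected because it concerns the primary endpoint, stands in both documents and supports a rule for ending recruitment.

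**What to change.** In the protocol's sample-size paragraph and in SAP 2.3:

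1. State the requirement as 112 per group, 224 in total.
2. State the power delivered at the planned sizes: about 65% with 150 randomised and about 55% with 56 per group, at 90% healing in both arms, a 10-percentage-point margin, one-sided 0.05 and no missing outcomes.
3. Remove the statement that 56 per group satisfies the calculation. If the fallback stays, give feasibility as its ground.
4. Add that failure to show non-inferiority at these sizes would be inconclusive.

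The cost is a wording amendment to one paragraph in each document and a less favourable stated power. Correcting the figures requires no additional participants; whether to enrol more is for the sponsor to decide separately.

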2.4 FRAMEWORK

The primary outcome will be tested according to the non-inferiority hypothesis testing framework. All secondary outcomes will be tested according to the superiority hypothesis testing framework.

2.5 STATISTICAL INTERIM ANALYSES AND STOPPING GUIDANCE

One interim analysis will be conducted after the primary outcome (proportion of healed ulcers at 12 weeks) has been observed in 30 participants in each study arm. The analysis will be conducted according to the intention-to-treat (ITT) approach, that is, all participants randomized will be analyzed according to their intended study group. If a two-sided Chi-square test demonstrates a statistically significant difference between the groups on the 0.001 level (relative risk, risk difference and odds ratio (OR) with confidence intervals (CI) will also be calculated) recruitment of new participants will be stopped but the follow-up of participants who already are enrolled in the study will continue. If the Chi-square test is not significant (that is, $p > 0.001$), recruitment of new participants will continue as planned. The significance level will not be adjusted due to the interim analysis as only one interim analysis is conducted.

2.6 TIMING OF FINAL ANALYSIS

The short-term outcomes, that is, healing, adverse events and adverse device effects during treatment, will be analyzed and published after the required number of participants have ended the treatment period.

The long-term outcomes, that is, up to 12 months after treatment end, will be analyzed and published after that every included participant has either been assessed for 12 months outcomes or has been lost to follow-up.

2.7 TIMING OF OUTCOME ASSESSMENTS

Table 1 below lists outcomes and time points for assessments (base-line, 4 weeks into treatment, and 1, 6 and 12 months after treatment end). For the 4 week into treatment and 1 month post-treatment assessments, a visit window of ± 1 week will be used. For the 6 and 12 months post-treatment assessments, a visit window of ± 1 month will be used.

Table 1. Overview of variables and assessment methods.

Variable (scale level: nominal=N, ordinal=O, interval=I)	Assessment method	Assessment occasion				
		Treatment period		Follow-up after treatment end		
		Base- line	4 weeks	1 month	6 months	12 months
Ulcer healing (N)	Clinical observation + blinded photo	X	X	X		
Skin complications (N)	Clinical observation + blinded photo	X	X	X		
Glycemic control (I)	Blood sample (HbA1c) ^a	X	X	X	X	X
BMI (I)	Measurement of weight and height	X	X	X	X	X
Gait function (I)	10 meter walk test ^{b 17}	X	X	X	X	X
Gait function (I)	Timed up and go ^{b 18}	X	X	X	X	X
Balance (O)	Berg balance scale ^{b 19}	X	X	X	X	X
Muscle atrophy (I)	Calf circumference ^{a 20}	X	X	X	X	X
General quality of life (O)	RAND-36 ^{c 21} , EQ-5D-5L ^{c 22}	X	X	X	X	X
Disease-specific quality of life (O)	DFS-SF ^{c 23}	X	X	X	X	X
Physical activity (I)	ActivPAL ^{d 24}	X	X	X	X	X
Physical activity (O)	National Board of Health and Welfare's indicator questions ²⁵	X	X	X	X	X
Bone mass density (I)	DXA ^e (heel bone)	X		X	X	X
Locus of control (O)	Questions from MHLC-C ^{c 26}	X		X	X	X
Ankle range of motion (I)	Goniometer ^{a 27}	X		X	X	X
Ankle strength (I)	Dynamometer ^{a 28}	X		X	X	X
Adherence to therapeutic shoes (O)	Questions from Q-TFA ^{c 29}	X		X	X	X
Treatment satisfaction (O)	Visual analogue scale ^c		X	X		
New ulcers, amputations, death, Charcot foot (N)	Patient file and self-report ^c				X	X
Health care consumption (O) ^f	Patient administration systems and self-report ^c			X	X	X
Sick leave from work (I) ^f	Self-report, ^c Swedish Social Insurance Agency's system			X	X	X

^aStandardized method, ^bfunction test, ^cquestionnaire, ^dactivity monitor, ^eDual-energy X-ray absorptiometry ^ffor the of health-economic analysis.

3 STATISTICAL PRINCIPLES

3.1 CONFIDENCE INTERVALS AND P VALUES

In all analyses a 95% confidence level will be used as a cut off to declare statistical significance, and report both exact p-values and 95% CI. One-sided tests and CI will be used for the primary outcome and two-sided tests and CI the secondary outcomes. No adjustment for multiple comparisons will be used.

3.2 ADHERENCE AND PROTOCOL DEVIATIONS

Adherence to the interventions (sealed shoe and TCC) is defined as continuous use of the devices during the treatment period. If a person treated with TCC removes the device on one or more occasions or refuses to continue treatment this will be considered non-adherence. If a person treated with a sealed shoe removes the device (assessed by inspecting if the seal has been broken) on one or more occasions or refuses to continue treatment this will be considered non-adherence.

Non-adherence will be presented per type of non-adherence and frequency. All types of non-adherence will be presented as number and percentage. In addition, removal of devices will be presented as means and standard deviation.

A protocol deviation is defined as a failure to adhere to the protocol such as the wrong intervention being administered, incorrect data being collected and documented, errors in applying inclusion/exclusion criteria or missed follow-up visits. This will be presented as number and type, per study group.

3.3 ANALYSIS POPULATIONS

The primary outcome (ulcer healing) will be analyzed both on the ITT dataset, that is, on all randomized participants, and on the per protocol dataset, including only patients who were exposed to the intended intervention at least 80% of the treatment days, as judged per above (point 3.2). Secondary outcomes (including adverse events and adverse device effects) will only be analyzed on the ITT dataset.

